5.2 Recruitment Methods

- State how many subjects will be needed.
- Describe when, where, how and by whom potential subjects will be identified and recruited.
- Describe materials that will be used to recruit subjects, e.g., advertisements. Include materials as an appendix or separate attachment.

- Describe any payments to subjects, including the amount, timing (at the end of the study or pro-rated for partial study participation), method (e.g., cash, check, gift card), and whether subjects will experience a delay in receiving the payment.

We will recruit 54 gender-balanced veterans in the following three groups: 1) with chronic, non-specific LBP and a Roland-Morris Disability Questionnaire (RMDQ) score of >12 (n=18), 2) with chronic, non-specific LBP and a RMDQ score of ≤12 (n=18), 3) asymptomatic and no a recent history of non-specific LBP (n=18; serving as control group)

Participants will primarily be recruited from veteran populations receiving treatments at the Lexington VA Medical Center in Lexington, KY. This center has two facilities and several community-based clinics in the surrounding areas, and serves a population of more than 92,000 veterans. Veteran population in our local communities who do not receive care at the Lexington VA Medical Center will also be recruited. [name] (Co-I) from the Department of Physical Medicine and Rehabilitation, with assistance from [name] (Clinical Research Assistant), will lead our patient recruitment efforts.

Recruitment will be done between months 6 and 18 of the project period. During this period, PI and Co-I will meet providers that see patients with LBP to seek their assistance in identification of patients with LBP. This will include, but not limited to, primary care physicians, physical therapist, chiropractors, acupuncturists, and etc., to inform them about the study and target patient population. These providers will be asked to inform their potentially eligible patients about our study and give them our IRB approved recruitment flyer. In addition to posting flyers in these clinics, we will have one of our research staff to be present in select days to provide more information to the interested patients. We will also distribute our study flyers to local institutions that serve Veterans. The distribution of study flyers will also include the use of listservs that will be sent to Veterans who are studying at the University of Kentucky.

The recruitment flyer describes the main inclusion/exclusion criteria, contact information of the PI, location and duration of experiments and the amount of compensation.

Participants will be compensated for their time and efforts in participating in the study for a total of \$40.

5.3 Informed Consent Procedures

- Indicate if informed consent will be obtained and/or if you are requesting a waiver of informed consent or waiver of documentation of informed consent. If the research involves multiple phases, specify for which phases of the research the waiver(s) is being requested and/or the informed consent will be sought.
- Describe who will be obtaining informed consent, if applicable, and any circumstances that may need to be addressed (e.g. subjects with impaired decision making ability and the use of a legally authorized representative, etc.)

- If applicable, indicate how local site study personnel will be trained regarding human subjects protections requirements and how to obtain and document informed consent.

This project requires written documentation of informed consent from all study participants. Approval of the informed consent document, the study protocol, and recruitment materials will be obtained before data collection begins. During the informed consent process, research personnel will explain the handling of data and personal health information and guide potential participants through the study consent form. Additionally, study staff will explain the study requirements and provide a study flow chart and information sheet to the potential participant. This will include an explanation of the interview time commitments and biomechanical assessments, potential risks of participation, potential benefits of participation, what to do if an adverse event occurs, and the option for discontinuation of study participation. Participants will be informed that they may choose to stop participating in the study at any stage. Once informed consent is administered, both the participant and research personnel will sign and date the consent form. A copy of the consent form will be provided to the participant.

Finally, all study personnel will have up-to-date training in human subject's protection and study procedures.

5.4 Inclusion/Exclusion Criteria

- Describe the criteria that determine who will be included in or excluded from the study.

Inclusion/Exclusion Criteria			
	Group-1	Group-2	Group-3
Current condition	Non-specific LBP	Non-specific LBP	Asymptomatic
LBP Experience	Chronic*	Chronic*	No recent history
RMDQ score	>12	≤12	N/A
Pain severity (0-9)	≥2	≥2	N/A
Inclusion criteria	
 • Age between 21 and 70 years old • Body mass index between 18 and 32 		
Exclusion criteria	
 • Any spinal surgery [e.g., spinal fusion surgery] • Any abnormalities in lower extremity joints due to disease or injury that would likely affects lower back mechanics [e.g., lower limb amputation or peripheral arterial disease] • Any safety concern [e.g., pregnancy] • Any medical condition for which we can't determine the impact of our experimental procedures. [e.g., we don't know whether our measurement instrument will affect pacemakers.] • Inability to read or verbally comprehend English • Unwilling or unable to comply with study protocol • Retention of legal advice or an open / pending legal case related to 		

	LBP

 • Definition recommended by the NIH task force on research standards for chronic LBP will be used: a pain in the lower back on more than half of days over the past 6 months. 	

Eligibility of participants will be determined in a two-step screening procedure involving an initial brief screening followed by an on-site screening. The brief screening will be done over phone for participants who contact the study personnel via information given in the flyer or it will be done in the clinic by the research staff who will be present in clinic for participant recruitment. During the brief screening an overview of study objectives and procedures will be provided, and the following provisional eligibility criteria will be verified:

- Age between 21 and 70 years
- Body mass index between 18 and 32, calculated using self-report of weight and height
- Current, a recent history, or no recent history of LBP
- Any spinal surgery [e.g., *spinal fusion surgery*]
- Any abnormalities in lower extremity joints due to disease or injury that would likely affects lower back mechanics [e.g., *lower limb amputation or peripheral arterial disease*]
- Any safety concern [e.g., *pregnancy*]
- Any medical condition for which we can't determine the impact of our experimental procedures. [e.g., *we don't know whether our measurement instrument will affect pacemakers.*]
- Inability to read or verbally comprehend English
- Retention of legal advice or an open / pending legal case related to LBP

Those who are provisionally eligible and still interested will then complete an on-site screening, consisting of informed consent process and final eligibility screening. [name] (Co-I) will oversee the on-site screening. [name] (PI) together with [name] (Co-I) will then review the results of each screening and decide about the eligibility of the participants. Participants deemed eligible will be scheduled for the data collection which can also take place immediately after eligibility determination. The study will be conducted in a newly developed lab for studies of the human musculoskeletal biomechanics that will be directed by [name].

5.5 Study Evaluations

- **Describe all evaluations to be conducted (including screening; tests/questionnaires that will be administered; any procedures that subjects will be required to complete) and data collection methods. Include materials as an appendix or separate attachment.**

In each data collection session, participants will first be instrumented with sensors to enable measurement of kinematics and muscle activity, similar to procedures we used in our earlier studies.⁷⁰⁻⁷³ Specifically, wireless inertial measurement units (Xsens MTW, Xsens Technologies, Enschede, Netherlands)⁷⁴ will be used to measure rotations of the thorax and pelvis, and surface EMG electrodes will be used to measure the activity of erector spinae, rectus abdominus, internal and external obliques. Participants will then be asked to stand on a force plate and perform a forward bending and backward return test.^{38, 72, 75} Participants will be instructed to bend from an upright standing posture to their maximum comfortable forward bending posture and then return to the upright posture at a self-selected pace. Participants will then be instructed to perform the following activities of daily life at a self-selected pace: walking on level^{76, 77} surfaces, sit-to-stand and stand-to-sit motions,⁷⁹ and lowering and lifting a 10 lb load to their knee height.⁸⁰ These activities have been selected because they represent basic

but repetitive activities of daily life, and we have successfully used them in our earlier investigation of spinal loads among asymptomatic non-veterans, as well as persons with unilateral lower limb amputation. Finally, sudden perturbation followed by stress-relaxation tests will be conducted as in earlier studies and as explained below. Each of the above tests will take less than 5 minutes, and we will provide break periods between each set of tests to minimize fatigue and discomfort.

In preparation for future projects, we will also administer the following questionnaires that are relevant to LBP experience during the data collection session: 1) comprehensive health status using the PROMIS-29 questionnaire⁸¹ (*[all participants]*), 2) survey of habitual physical activity⁸² (*all participants*), 3) the short version of Copenhagen Psychosocial questionnaire concerning work and non-work-related factors⁸³ (*all participants*), [4] *the minimum data set recommended by the NIH task force on research standards for chronic LBP (only veterans with LBP)*, 5) pain intensity using a numerical rating scale⁸⁴ (*only veterans with LBP*), 6) LBP-related disability using the 24-item Roland Morris Disability Questionnaire⁸⁵ (*only veterans with LBP*), 7) the fear-avoidance beliefs questionnaire⁸⁶ (*only veterans with LBP*), pain catastrophizing scale questionnaire (*only veterans with LBP*), and pain self-efficacy questionnaire (*only veterans with LBP*). Total time for the entire data collection session, including the instrumentation time, is estimated to be less than 3 hours.

Characterization of lower back MB: Sudden perturbation and stress-relaxation tests will be used to characterize [*bulk*] active and passive aspects of lower back MB. Sudden perturbation tests will be conducted in a displacement-control manner that we have developed, which provides separate quantification of both active reflexive and intrinsic stiffness of the lower back.^{71, 73} Here, intrinsic stiffness refers to aspects of lower back MBs that are quantified during the reflex delay period (i.e., between perturbation onset and reflexive muscle response), and which incorporate both passive and active contributions of lower back tissues. However, the passive contribution of tissues to intrinsic stiffness in upright standing posture (i.e., the position used in our experimental setting) is minimal;⁸⁷ therefore, intrinsic stiffness primarily reflects the contribution of background muscle activities.

During the sudden perturbation test, participants will stand in a metal frame that restrains the pelvis and lower limbs [*to isolate the lower back response*] (**Fig. 1**). Horizontal position perturbations, generated by a servomotor (Kollmorgen AKM53K, Radford, VA, USA), are transmitted to the trunk (T8) via a rigid harness-rod system. A one-minute sequence of anteroposterior trunk displacements (± 5 mm) is induced with a pseudo-random set of delays between each. The driving force during the perturbations will be measured using an in-line load cell (Interface SM2000, Scottsdale, AZ, USA) located next to the motor, whereas the resulting kinematics (small displacements with high accelerations) will be measured using two laser displacement sensors (Optex FA, Kyoto, Japan), with one targeting the back of the harness at the T8 level, and the other targeting the load cell.

[figure not shown]

Figure 2. Setup for the trunk stress-relaxation tests.

[figure not shown]

Figure 1. Setup for the trunk perturbation and stress-relaxation tests.

The sudden perturbation frame is designed so that trunk flexion can be achieved by raising the participant's legs/pelvis using an actuator (**Fig. 2**); rotation of the lower body is about the L5-S1 while the trunk is kept upright. Accordingly, the stress-relaxation tests will be conducted in the same setup used for the perturbation tests, by

rotating the participant's legs around his/her lower back using an actuated platform.^{70, 88} The lower extremities and the pelvis of participants will be constrained to the platform and the thorax position will be fixed (Fig. 2). Therefore, the amount of lumbar flexion will be the same as the amount of platform rotation. During stress-relaxation tests, we will specifically rotate the leg platform to the extent that it generates 70% of the lumbar flexion angle that can be achieved during a trunk forward bending and backward return activity, as described in §2.6. This posture will be maintained for 4 minutes, during which trunk resistance (via load cell) will be measured. We have extensively used the methods proposed here in our earlier studies of asymptomatic individuals^{56, 57, 70, 88} and persons with unilateral lower limb amputation.⁵⁵ Our sudden perturbation and stress-relaxation tests yield excellent within-day (ICC>0.85) and moderate-high between-day (ICC=0.5-0.8) reproducibility of measures of lower back MB.⁶⁶

Estimation of spinal loads: The computational strategy that will be used to estimate spinal loads is our non-linear finite element (FE) model of the spine that, accounting for passive contribution of lower back tissues, can estimate the required muscle forces to complete a particular task using an optimization-based iterative procedure.⁸⁹ This advanced kinematics-driven FE model can provide a more nuanced approach to revealing the foundations of spinal loads in relation to LBP, and addresses several important shortcomings

of existing models. For instance, geometrical nonlinearities have been included in our model by representing the spine as a set of flexible beam elements that mimic intervertebral discs and rigid elements that mimic the thorax and lumbar vertebrae (Fig. 3). Material nonlinearities are also considered in our model by incorporation of intervertebral disc stiffness using nonlinear axial compression-strain relationships, along with moment-rotation relationships in the sagittal/coronal/transverse planes that have been obtained from earlier numerical and experimental studies of lumbar spine motion segments.⁹⁰⁻⁹²

Other modeling approaches generally predict trunk muscle forces on the basis of satisfying equilibrium at only one spinal level (i.e., often at the L4-L5 or L5-S1),^{64, 93, 94} and therefore result in the prediction of muscle forces that violate equilibrium requirements at other spinal levels.⁹⁵ In our improved model, muscle forces are estimated such that equilibrium requirements are satisfied across the entire lumbar spine. Our model also includes a detailed trunk muscle architecture (Fig. 3), wherein muscle wrapping around underlying tissues is considered.⁹⁶ The muscle architecture in our computational model includes 56 muscles (Fig. 3); 46 muscles connecting the lumbar vertebrae to the pelvis (i.e., local muscles), and 10 muscles connecting the thoracic spine/rib cage to the pelvis (i.e., global muscles). To determine the required muscle forces for the satisfaction of equilibrium across the entire lumbar spine, segmental kinematics in the lumbar region are required. Since only whole-body level kinematics data are available from experimental measurements, a heuristic optimization procedure will be used with our model to determine a set of segmental kinematics in the lumbar region (i.e., from L1 to L5), such that the corresponding set of predicted muscle forces minimize a cost function.⁹⁷ The cost function that will be used for this heuristic optimization procedure will be the sum of squared muscle stress

[figure not shown]

Figure 3. FE model of the trunk. Spine geometry and material properties (left), and lateral/sagittal views of muscle architecture (right).

across all 56 lower back muscles. We have recently published a detailed description of this procedure in Journal of Biomechanics.⁹⁷ Predictions of lumbar segmental kinematics from this model provide good-excellent agreement with those from image-based measurements.⁹⁷ The associated muscle forces with the optimal local kinematics will then be used to determine spinal loads at all lumbar levels. This heuristic optimization procedure was developed in Matlab (The MathWorks Inc., Natick, MA, version 7.13), and FE simulations will be conducted in Abaqus/CAE (Version 2018, Dassault Systemes Simulia, Providence, RI).

We have used our FE computational model extensively to study occupational risk factors for LBP, including manual material handling,^{35, 98} trunk motion at different velocities,⁸⁹ whole body vibration,⁹⁹ impact,¹⁰⁰ and sudden loading/unloading.^{101, 102} The bio-fidelity of our model-based predictions of trunk muscle forces and spinal loads has been demonstrated both in static and dynamic situations. More specifically, good-to-excellent correlations were found between model predictions and measured trunk muscle activity ($R>0.7$),¹⁰¹ with measured ground reaction forces ($R>0.8$),⁸⁹ and with measured trunk resistance to sudden loading ($R>0.8$ unpublished data from¹⁰³). In an ongoing collaboration with Walter-Reed National Military Medical Center, we are using our model to estimate spinal loads in service members with and without unilateral lower limb amputation while they performed activities similar to those proposed in this project.⁷⁶⁻⁷⁹

Data analyses- Aim-1: From the perturbation tests, we will obtain three outcome measures: reflex latency (t), intrinsic stiffness (K_{IN}), and maximum reflexive force (F_{REF}). Latency of reflexive responses of trunk muscles will be estimated using a system identification approach and by relating muscle activity to trunk displacement.⁷¹ Intrinsic stiffness will be estimated using a system identification procedure, and by relating trunk kinematics with trunk kinetics, respectively, from displacement sensors and load cell obtained during the latency period.⁷³ To obtain the maximum reflexive force, the reflexive responses of lower back will be estimated by subtracting the intrinsic response from the measured trunk response (i.e., reaction force from load cell) over a time window between the end of latency period and 150 msec post perturbation.⁵⁷ From the stress-relaxation test, we will obtain the average passive stiffness (K_p) and viscoelastic relaxation (R) of lower back tissues as shown in **Figure 4**.^{70, 88}

Data analyses-Aim-2: Outputs of FE simulations of daily activities will include forces in 56 trunk muscles and spinal loads at all lumbar spine levels.^{98, 99, 102} These outputs will be estimated for each instance of each simulated activity described in §2.6. To facilitate quantitative comparison, and considering that maximum spinal load at each instant often occurs at the lowermost level of the lumbar spine, we will extract the maximum spinal load experienced at the L5-S1 level during each activity. The measure of spinal load for each participant will then be calculated as follows for statistical analyses: $SL = \text{norm}(\sum_{activity=1}^5 SL_{activity})$ wherein *norm* denotes the magnitude of vector summation and $SL_{activity}$ denotes the maximum spinal load under each activity.

[figure not shown]

Figure 4. The slope of loading side and the moment drop on the relaxation sides of curve denote respectively average passive stiffness (K_{ave}) and viscoelastic relaxation (R). Adopted from ref #66.

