We have implemented all of the proposed biomechanical methods in this application in our earlier studies of asymptomatic individuals (see Research Approach). However, the proposed sudden perturbation and stress-relaxation tests will be done on patients with LBP for the first time in our lab. Similar tests on patients with LBP have been reported in the literature,⁷⁰⁻⁷² therefore, we do not expect failure in the conduct of the proposed tests. It is of note that our perturbation testing device has several redundant safety measures. Participants hold a safety switch, which must be depressed to activate testing equipment. Testing is immediately discontinued due to electrical power loss if the participant releases the safety switch. Participants will be instructed to release the switch and de-activate testing equipment if they experience discomfort during the perturbation. The perturbation test has a limit stop switch that cuts all power to the motor if the motor rotates more than 60 degrees past its normal range, limiting accidental perturbation to approximately 2cm. A manual emergency power switch is located on the front of the frame, reachable both by participants and study personnel, with additional power switches on the electrical power box and within the computer software that controls the motor. Finally during the stress-relaxation test, the participant's leg will be raised using a slow speed (3 deg/second) actuator which can be stopped immediately at subject's request.

Direct benefits to the subjects are minimal; in particular, there are no immediate health benefits of participating in the proposed study. A potential indirect benefit is further the understanding of LBP for patient veterans.

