5.6 Statistical Analysis

- What statistical test will be done?
- Provide sample size determination and analysis (include anticipated rate of screen failures, study discontinuations, lost to follow-up etc.).
- Describe how, where and by whom the data will be analyzed.

For each measure (i.e., reflexive latency, intrinsic stiffness, reflexive force, passive stiffness, and stress relaxation from Aim 1, along with the spinal load, SL , from Aim 2), we will run a univariate analysis of variance to verify potential differences between study groups (i.e., independent factor: participant group with five levels). A significant ANOVA will be followed with post-hoc pairwise comparison using Bonferroni's procedures. Prior to these analyses, parametric assumptions will be evaluated. As needed, data transformations will be used, or a non-parametric approach will be employed.

The statistical analyses will be led by the PI will be overseen by [name]

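### Relaxation R is compared across groups tested at person-specific flexion angles; unless R is scaled and the angle reported, a group difference in R cannot be read as a difference in tissue

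*Combined protocol and SAP*

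**What the plan says.** Section 5.5 (Characterization of lower back MB) sets the stress-relaxation angle individually: "we will specifically rotate the leg platform to the extent that it generates 70% of the lumbar flexion angle that can be achieved" in the forward bending test. In that test, described earlier in section 5.5, participants "bend from an upright standing posture to their maximum comfortable forward bending posture" at their own pace. The imposed angle is known for each person, because "the amount of lumbar flexion will be the same as the amount of platform rotation". Section 5.1 gives the loading rate: the participant's "leg will be raised using a slow speed (3 deg/second) actuator". On the hold, section 5.5 says: "This posture will be maintained for 4 minutes, during which trunk resistance (via load cell) will be measured".

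Under the Aim 1 data analyses, "we will obtain the average passive stiffness (K_p) and viscoelastic relaxation (R) of lower back tissues". The Figure 4 caption explains the two measures: "The slope of loading side and the moment drop on the relaxation sides of curve denote respectively average passive stiffness" and viscoelastic relaxation. For each measure, section 5.6 says "we will run a univariate analysis of variance to verify potential differences between study groups", with participant group as the only stated factor. The visible text does not mention dividing R by peak moment or angle, using the angle as a covariate, or describing the angle by group.

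**The concern.** A moment drop depends on how far the tissue was stretched as well as on how the tissue relaxes. The stretch here is a fixed share of a range that ends at comfort. Two groups have current LBP and the third is asymptomatic, so pain or guarding could set the test amplitude. If it does, R as captioned mixes imposed angle with tissue behaviour, and the planned ANOVA cannot separate them.

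What is at stake is interpretation. Section 5.5 describes R as a property of lower back tissues, and a smaller drop in the LBP groups would naturally be read that way. The three perturbation measures use a fixed displacement of 5 mm in each direction and do not have this problem.

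**Working it through.** The plan gives no lumbar angle, stiffness or relaxation value, so it has no figure of its own to reproduce here. The calculation below is an illustration.

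**Inputs from the documents:** 70% test level, 3 deg/s ramp, 4-minute (240 s) hold, 18 per group, three groups, significance level 0.05. Section 5.6 writes five group levels; the design has three, and three are used here.

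**Assumed inputs:** control maximum flexion 60 degrees, so a test angle of 0.70 × 60 = 42 degrees; both LBP groups at a fraction r = 0.90 or 0.75 of that; identical linear tissue in all groups; relaxing fraction g = 0.3-0.4; time constant τ = 5-100 s; between-person CV of R 30-50%.

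**Model.** Ramp time is T = angle / 3: 14 s for controls, 12.6 s at r = 0.90 and 10.5 s at r = 0.75. Up to a common constant:

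- moment at start of hold: M = (1 − g)T + gτ(1 − e^(−T/τ))
- drop over the hold: D = gτ(1 − e^(−T/τ))(1 − e^(−240/τ))
- percent relaxation: D / M
- average stiffness: M / T

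The LBP/control ratio of drops is therefore (1 − e^(−rT/τ)) / (1 − e^(−T/τ)), with T = 14. For r = 0.75 and τ = 5 this is (1 − e^(−2.1)) / (1 − e^(−2.8)) = 0.878 / 0.939 = 0.934. For τ = 100 it is 0.0997 / 0.1306 = 0.763.

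| τ (s) | Drop ratio, r = 0.90 | Drop ratio, r = 0.75 | Percent ratio, r = 0.75 | Stiffness ratio, r = 0.75 |
|---|---|---|---|---|
| 5 | 0.979 | 0.934 | 1.19-1.21 | 1.03-1.045 |
| 10 | 0.951 | 0.863 | 1.11-1.12 | 1.03-1.04 |
| 30 | 0.920 | 0.792 | 1.04 | 1.01-1.02 |
| 100 | 0.906 | 0.763 | 1.01 | 1.01 |

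With no tissue difference, the drop is 2-9% lower (r = 0.90) or 7-24% lower (r = 0.75). Stiffness moves by at most about 4.5%.

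**Effect on the ANOVA.** The spurious standardised shift is δ = (1 − drop ratio) / CV. With both LBP groups shifted by δ, the noncentrality is 18 × (2/3)δ² = 12δ², on F(2, 51).

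- r = 0.90: δ = 0.04-0.31, probability of significance 5-14%.
- r = 0.75: δ = 0.13-0.79, probability of significance 7-66%.

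**Sensitivity of the upper corner** (r = 0.75, τ = 100 s, CV 30%, δ = 0.79, noncentrality 7.5, 66%). If Group 2 has half the shift, the noncentrality is 9δ² = 5.6 and the probability 53%. If instead the CV is 60%, δ = 0.395 and the probability is 20%.

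**Second calculation with a simpler model.** The drop is taken as proportional to angle. Control maximum flexion is assumed to be 50 degrees (SD 10), with Group 1 lower by 10 degrees and Group 2 by 5, and tissue CV 20-40%. The unscaled drop is significant in 22-47% of simulated studies, against about 5% with no angle shift. Stiffness stays at about 5% if tissue is linear.

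**The case against.** Several points on the other side stand.

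- **R may already be scaled.** The definition refers to a figure that is not shown and to cited method papers. The caption favours an unscaled drop but is not a formula. A reader might infer that the plan fails to scale R; the documents do not support that as a fact.
- **The angle difference is a premise.** No angle is reported by group. The Introduction cites a larger pelvic share of trunk motion in LBP, which is not the same as a smaller maximum lumbar angle. Section 5.1 says the lab has not yet run this test in patients with LBP, so its own experience does not settle the matter either way.
- **The test design is legitimate.** Loading each person to the same share of their own range is a recognised approach, and nothing here argues for a fixed angle.
- **Planning value is preserved.** The sample size justification says the study is to supply effect sizes for future grants. A reader might infer that an angle artefact would spoil them. It would not for a later study using the same 70% protocol and outcome, where the observed effect size is the relevant input whatever its mechanism.
- **Stiffness should not carry equal weight.** A slope is already per degree. The nonlinearity described in section 5.5 belongs to the finite element model; the documents do not establish it for the bulk lower back.
- **Percent relaxation is imperfect.** Ramp time varies with angle. In simulation with linear tissue, 25% smaller angles and a 5 s time constant, percent relaxation was falsely significant in 19-41% of studies, against 7-10% for the drop.

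The study's disclaimer of hypotheses and adequate power does not answer the interpretive point, because showing that these measures are sensitive to abnormality is its stated object.

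**Conclusion.** The point holds, conditionally and mainly for R. If R is the unscaled drop that the caption suggests, and if test angles differ by group, a group difference in R cannot be attributed to lower back tissues under the planned analysis. The size is unknown. The probabilities in the working rest wholly on assumed angles, time constants and CVs; at a 10% smaller angle they lie close to nominal, and the 66% figure is an extreme corner. This is a low-cost safeguard on interpretation, worth considering, and not a flaw in the test design.

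**What to change.** Leave the test procedure unchanged and add to section 5.6:

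1. Report platform rotation angle by group (mean, SD). It must be known to run the test, so no new measurement is needed.
2. State how R is computed. Unless it is already scaled, analyse relaxation as a percent of the moment at the start of the hold beside the planned drop, and give both effect sizes with 95% confidence intervals.
3. If angles differ by group, do not present the unscaled drop alone as a tissue difference.

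Optional sensitivity analyses are stiffness over one pre-specified common flexion window, and adjustment for angle. Adjustment should stay secondary, because angle may be a consequence of LBP and adjusting could remove a real difference. The window analysis would lose participants who do not reach its upper end, and they may not be a random subset.

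The cost is a few lines of wording and a little analysis. Percent relaxation is not fully angle-free: under assumed linear tissue and 25% smaller angles it is about 1-4% too high for time constants of 30 s or more, and about 20% too high at 5 s. It should therefore supplement the planned drop and not replace it.
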